STU#: 00208846

PROTOCOL TITLE: Intraoperative Use of Intravenous Indocyanine Green (ICG) to Assess Ovarian Perfusion Using Infrared Imaging: A Feasibility Pilot Study

PRINCIPAL INVESTIGATOR:

[name], MS
 Department of Obstetrics and Gynecology
 Northwestern University Feinberg School of Medicine
 [name]
 [name]
 [contact]
 [contact]

CO-INVESTIGATORS:

[name]
 Department of Obstetrics and Gynecology
 Northwestern University Feinberg School of Medicine
 [name]
 [contact]
 [contact]

VERSION NUMBER:

Version 2

VERSION DATE:

June 8, 2020

STUDY SUMMARY:

Investigational Agent(s) (Drugs or Devices)	Indocyanine green (ICG)
IND / IDE / HDE #	
Indicate Special Population(s)	 Children  Children who are wards of the state  Adults Unable to Consent  Cognitively Impaired Adults  Neonates of Uncertain Viability  Pregnant Women  Prisoners (or other detained/paroled individuals)  Students/Employees  N/A
Sample Size	30
Funding Source	Karl Storz
Indicate the type of consent to be obtained	 Written  Verbal/Waiver of Documentation of Informed Consent  Waiver of HIPAA Authorization  Waiver/Alteration of Consent Process
Site	 Lead Site (For A Multiple Site Research Study)

STU#: 00208846

	 Data Coordinating Center (DCC)
Research Related Radiation Exposure	 Yes  No
DSMB / DMC / IDMC	 Yes  No

1.0 OBJECTIVES:

To assess the feasibility of using intravenous ICG to characterize the vascular perfusion of ovaries during gynecologic surgery.

2.0 BACKGROUND:

2.1 Chemistry

Modern surgical techniques have incorporated the use functional imaging to better identify and target areas of interest. Indocyanine green (ICG) is a Food and Drug (FDA)-approved tricarboyanine dye that is fluorescent under near-infrared (NIR) light. Excitation of ICG occurs between 750 and 800 nm. Its chemical formula is C₄₃H₄₇N₂NaO₆S₂ (Han, Kankala, Wang, & Chen, 2018). ICG solutions for injection often contain sodium iodide. ICG is water soluble and when introduced intravenously, it is bound by plasma proteins, namely albumin. The intravascular half-life of ICG is 3-4 minutes with rapid hepatic clearance (Cherrick, Stein, Leevy, & Davidson, 1960). Clearance of ICG follows first-order kinetics and is eliminated exponentially in the first 10-20 minutes after administration. Trace amounts of ICG can remain in the system for more than an hour. ICG has no known metabolites (Alander et al., 2012). The LD₅₀ (lethal dose) of ICG is 50 – 80 mg/kg which is significantly greater than standard doses of less than 2 mg/kg (KARL STORZ Endoscopy - America, 2016). Rapid clearance of the dye allows it to be given over multiple injections, as needed, during a single procedure. After intravenous injection ICG is visible in organs within 1-2 minutes and remains visible for 20-120 minutes depending upon the organ of interest (KARL STORZ Endoscopy - America, 2016).

2.2 Clinical uses

Since the 1950s, ICG has been approved in the United States for intravenous administration. Early uses for ICG included measurement of hepatic function, cardiac output and retinal angiography (Rahimtoola & Swan, 1965; Yannuzzi, 2011). Today, ICG has been applied across several surgical specialties to improve intraoperative assessment and to reduce unnecessary tissue trauma. These uses are off-label but are a part of a growing body of literature that suggests ICG can be useful in assessments of tissue and organ perfusion. Selective sentinel lymph node resection is based on the observation that dye injected into tumor or tumor-adjacent tissues is taken up into the lymphatic system. The first lymph nodes to undergo dye uptake are known as sentinel lymph nodes and are representative of other lymph nodes within the same lymphatic chain. A dye negative SLN is proxy for a tumor free lymph node, making radical lymphadenectomy unnecessary and reducing complications from such dissections. This SLN concept has been employed in surgical oncology for many disciplines including breast, cervical and endometrial cancer.

Another major surgical application is intraoperative angiography to evaluate for preserved or recovered vascular perfusion (Arichi et al., 2014; Ferroni, Sentell, & Abaza, 2018). ICG fluorescence angiography has also been employed in colorectal surgery to identify anastomotic insufficiency, or poor perfusion of anastomoses after bowel resection. In PILLAR II, a prospective, multicenter clinical trial in colorectal surgery, fluorescence angiography using ICG was successful in 99% of cases and changed surgical plans in 8% (Jafari et al., 2015). In hepatobiliary surgery, ICG facilitates the identification of biliary anatomy and of tumor as it accumulates within the lesion (Baiocchi, Diana, & Boni, 2018). In plastic surgery, ICG has been

STU#: 00208846

used to assess vascular anastomoses and tissue perfusion (de Vita & Buccheri, 2018). Neurosurgical uses of ICG have centered around the identification of vascular pathology (Reinhart, Huntington, Blair, Heniford, & Augenstein, 2016).

Gynecologic uses of ICG extend beyond tumor localization for cancer. Excisional endometriosis surgery may be technically challenging and the use of functional imaging can facilitate assessment of tissue perfusion after removal of lesions on the bowel or ovary (Bar-Shavit, Jaillet, Chauvet, Canis, & Bourdel, 2018). De Neef et al. used ICG intraoperatively to identify rectovaginal deep infiltrating endometriosis (DIE) (De Neef et al., 2018). They reported a series of 6 patients undergoing laparoscopy for endometriosis in which 0.25 mg/kg ICG was injected intravenously at the time of skin incision. Rectovaginal DIE was then targeted using surgical NIR imaging equipment. Rectovaginal DIE, and superficial endometriotic lesions on the peritoneum were identified in every case. No intra- or postoperative complications were reported. The clinical utility of ICG during bowel resection for endometriosis has also been suggested, allowing real-time visualization of bowel perfusion and aid in the selection of location of bowel transection (Seracchioli, Raimondo, Arena, Zanello, & Mabrouk, 2018).

The purpose of this study is to determine the feasibility of intravenous ICG administration to facilitate assessments of ovarian vascular perfusion. Historically, assessment of ovarian perfusion has been performed visually or via ultrasound with Doppler evaluation. In a study of infertile patients, ovarian perfusion was assessed using transvaginal ultrasound with Doppler (Kupesic & Kurjak, 1997). A resistance index (RI) was calculated based on vascular flow with differential results based on phase of the menstrual cycle or presence of ovarian pathology. In patients with ovarian endometriomas, evidence of ovarian interstitial microvascular injury has been demonstrated similarly by the presence of low flow and high RI (Qiu et al., 2012). The use of ICG to evaluate ovarian perfusion specifically has not been reported. The use of ICG for intraoperative perfusion assessment of the ovary could provide more information about the health of the ovary and inform the surgical approach to ovarian pathology.

2.3 Formulation

Indocyanine green for injection can be prepared by reconstituting one 25 mg vial of ICG using one 10 mL of sterile water. This mixture contains 2.5 mg of dye per mL of solution. ICG must be used within 6 hours after reconstitution.

2.4 Adverse effects

The most common adverse reactions that have been reported include allergic reactions that range from urticarial (hives) to anaphylaxis. Because of the sodium iodide presence in ICG contraindications include patients with a history of allergy to iodides due to the risk of anaphylaxis (Storz).

2.5 Drug interactions

Listed drug interactions include preparations containing sodium bisulfite which reduce the absorption peak of ICG (KARL STORZ Endoscopy - America, 2016)

3.0 STUDY ENDPOINTS:

3.1 Primary Objectives:

3.1.1 To assess the feasibility of using intravenous ICG to characterize the vascular perfusion of ovaries.

3.1.2 To utilize infrared light to image and detect adnexal ICG uptake.

STU#: 00208846

3.1.3 To qualitatively assess ovarian perfusion after ICG administration.

3.1.4 To quantitatively assess ovarian perfusion after ICG administration by analyzing the intensity of fluorescence on intraoperative imaging.

3.2 Secondary Objectives:

3.2.2 To qualitatively and quantitatively compare and contrast adnexal ICG uptake in the presence and absence of adnexal pathology.

4.0 STUDY INTERVENTION(S) / INVESTIGATIONAL AGENT(S):

ICG will be injected intravenously to assess ovarian perfusion in the presence or absence (control) of pathology. Near infrared fluorescence imaging will be used to illuminate the ICG. The extent of perfusion will be determined using digital imaging software.

ICG will be stored at the NM Investigational Pharmacy and administered intravenously by the anesthesiologist at the direction of the surgeon during surgical procedure.

5.0 PROCEDURES INVOLVED:

5.1.1 Patients who are scheduled to undergo surgery at Northwestern Memorial Hospital will be approached for recruitment of the study at their preoperative visit in the Center for Comprehensive Gynecology clinic. Research coordinator will review consent form with potential participant. Ample time will be left for participant questions and comprehension

5.2.1 The screening procedures include:

Informed consent: will be obtained for all potentially eligible participants. Once consented we will review subject eligibility referring to inclusion and exclusion criteria.

5.2.2 Medical History: Complete medical, surgical, gynecologic and obstetrical history, medications, allergies, social and family history.

5.2.3 Demographics

Age, gender, race, ethnicity, gravidity, parity.

5.2.4 Review previous and concomitant medications

5.2.5 Physical exam including vital signs (pulse and blood pressure), height and weight

5.3.1 Surgical Procedures Involved

Prior to injection, the ICG will be prepared under sterile conditions using a standard protocol for reconstitution that involves the following. One 25 mg vial of Indocyanine Green for Injection, USP will be reconstituted using one 10 mL Sterile Water for Injection, USP vial that is provided in the ICG for Injection Set. After reconstitution, each 25 mg vial of ICG contains 2.5 mg of dye per mL of solution. During surgery ICG will be administered intravenously via a peripheral or central line at the direction of the surgeon by the anesthesiologist. The injected amount will be a 3 mL solution of reconstituted ICG that contains a 7.5 mg dose of ICG. This will be followed by a 10 mL bolus of normal saline for injection per the manufacturer's recommendation. The total dose of dye injected should not exceed 2 mg/kg.

Visibility of the ICG fluorescence should occur within 1-2 minutes with a duration of 20-120 minutes (KARL STORZ Endoscopy - America, 2016)

STU#: 00208846

5.3.2 Imaging and Near-Infrared Devices: Karl Storz will provide the light source, device D-Light P and the NIR CCU Module, H3-Link on the equipment handler in the operating room. Images will be taken with two NIR camera heads (H3-Z FI) and light cables

5.4.1 Data Analysis

Images will be stored on locked Northwestern Memorial computers which only the study team will be able to access. Once imaging data is complete, study team will collect basic intensity quantification utilizing both *ImageJ* and Photoshop software.

6.0 DATA AND SPECIMEN BANKING

No specimens will be collected or banked for future use.

7.0 STUDY TIMELINES

7.1 Participants will be consented and enrolled at their pre-operative appointment

7.2 Study duration includes the time during ICG administration, visualization and imaging. Because this will be performed intraoperatively during standard survey of the abdomen and pelvis no surgical delays will be incurred. No other procedures or visits are necessary for participants in this study. If a participant seeks further treatment in the future at the Center for Comprehensive Gynecology, study coordinator will approach previous participant and consent them to participate in the study again.

7.3 Once imaging data is complete, study team will collect basic intensity quantification using *ImageJ* or *Photoshop*

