14.0 DATA MANAGEMENT AND CONFIDENTIALITY

STU#: 00208846

14.1 All collected data will be stored on a locked and secured Northwestern Memorial computer located in the Center for Comprehensive Gynecology. Only study team will have access to the data. Photos will be taken in the OR. Images will be collected after surgery and de-identified then uploaded into ImageJ and Photoshop for analysis. Only study team will conduct data analysis.

14.2 **Statistical procedures:** Images pixelation intensity will be assessed in ImageJ and Photoshop. A paired t-test will be used to assess a patient's ovary with pathology and the ovary without pathology to determine whether there are any differences in ICG intensity.

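### Does the single "or" in section 7.3, against "and" elsewhere, leave the program that measures fluorescence intensity undefined?

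*Protocol*

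**What the plan says.** Four places in the protocol name the software used to measure fluorescence.

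- Section 5.4.1 (Data Analysis): "study team will collect basic intensity quantification utilizing both *ImageJ* and Photoshop software".
- Section 7.3 (Study Timelines): "study team will collect basic intensity quantification using *ImageJ* or *Photoshop".
- Section 14.1 (Data Management): "Images will be collected after surgery and de-identified then uploaded into ImageJ and Photoshop for analysis".
- Section 14.2 (Statistical procedures): "Images pixelation intensity will be assessed in ImageJ and Photoshop".

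Section 4.0 is neutral: "The extent of perfusion will be determined using digital imaging software".

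The measurement serves two objectives. Primary objective 3.1.4 is "To quantitatively assess ovarian perfusion after ICG administration by analyzing the intensity of fluorescence on intraoperative imaging". Secondary objective 3.2.2 compares uptake with and without adnexal pathology. For that comparison section 14.2 specifies a paired t-test of a woman's ovary with pathology "and the ovary without pathology to determine whether there are any differences in ICG intensity". The planned enrolment is 30 (section 9.0), and the study is described as a feasibility pilot.

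**The concern.** Sections 5.4.1 and 7.3 describe the same step in nearly the same sentence, yet one requires both programs and the other appears to allow either. Intensity is the only quantitative measure that the protocol defines, and it is the variable in the only test that it names.

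Two kinds of harm are conceivable.

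1. If section 7.3 governed and *or* were exclusive, some women might be read in one program and some in the other. Their values might then not be comparable for objective 3.1.4.
2. If both programs are used and each gives its own value, there are two candidate results for the paired t-test. The more favourable one could be reported.

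Section 7.4 has images analysed as they become available, so a choice of program could be made with earlier results in view.

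**Working it through.** **The passages side by side.** The protocol gives no figure to reproduce here, so the first check is textual.

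| Section | Purpose of the section | Programs |
|---|---|---|
| 5.4.1 | how the data are analysed | both |
| 7.3 | when the step happens | one or the other |
| 14.1 | storage and de-identification | images uploaded to both |
| 14.2 | statistical procedures | both |

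The firm conflict is between 7.3 and the pair 5.4.1 and 14.2. Section 14.1 speaks only of uploading images for analysis. That fits two separate readings, and it equally fits one workflow with image handling in one program and measurement in the other. A team that uses both programs on every image meets 5.4.1, 14.1 and 14.2, and also meets 7.3 if *or* is inclusive. Only an exclusive *or* conflicts, and then 7.3 permits less than the analysis sections require.

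**Size of the harm.** The protocol states no significance level, no number of evaluable pairs and no agreement between the programs. Every input below is therefore an assumption.

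*Case 1: exclusive* or*, half the women read in each program, both ovaries of a woman in the same program.* Let one program read higher by a constant *o*, in units of the between-woman SD.

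- Paired difference: (Y_path + o) − (Y_none + o) = Y_path − Y_none. The offset cancels, so the t-test in 14.2 is unaffected.
- Between-woman SD for 3.1.4: the offset adds variance o² × ½ × ½ = o²/4, so the SD is multiplied by √(1 + o²/4).
  - o = 0.5: √1.0625 = 1.03, or 3% wider.
  - o = 1: √1.25 = 1.12, or 12% wider.

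*Case 2: both programs, each giving a value, with significance in either one counted.* Assume a two-sided 5% level, and let r_d be the correlation between the two programs' paired differences. The chance of at least one false positive is P(|Z₁| > 1.96 or |Z₂| > 1.96) for a bivariate normal pair. The last two columns give simulated paired t-tests (400,000 runs).

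| r_d | Normal | n = 10 | n = 30 |
|---|---|---|---|
| 0.90 | 0.070 | 0.073 | 0.071 |
| 0.95 | 0.065 | 0.066 | 0.065 |
| 0.99 | 0.057 | 0.058 | 0.056 |

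Differences can agree less well than single readings. Suppose readings correlate r, a woman's two ovaries correlate ρ, and reading errors are independent. Then r_d = (1 − ρ) / [(1 − ρ) + (1 − r)/r]. With ρ = 0.5:

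- r = 0.90: 0.5/(0.5 + 0.111) = 0.818; false-positive chance 0.077 (0.079 by simulation at 10 pairs).
- r = 0.95: 0.5/(0.5 + 0.053) = 0.905; chance 0.070.
- r = 0.99: 0.5/(0.5 + 0.010) = 0.980; chance 0.059.

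Across these assumptions the range is about 5.6-7.9%. If the two programs agree exactly, or form one workflow with a single value, there is no excess.

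**What each case says about section 7.3.** Case 2 arises under the wording of 5.4.1 and 14.2. Changing *or* to *and* in 7.3 would leave it exactly where it is. Only case 1 measures the disputed word, and it leaves the stated test untouched.

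**The case for a change.** The strongest case for a change is that the contradiction lies in the current text and is no mere variant of wording. Section 5.4.1 says *both* about the step that 7.3 describes with *or*, and the protocol itself fixes the software in both places. An analysis plan could name the value that enters the test, but the mismatch would remain. A pilot meant to prepare later studies benefits from a reproducible intensity measure, and the correction would cost one word.

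The mismatch does stand, and tidying it at the next opportunity would do no harm. Three things limit it.

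- For 7.3 to do damage, a line in the timelines would have to override the two sections that define the analysis.
- Offsets would fail to cancel in the t-test if one woman's two ovaries were read in different programs, but nothing in the protocol suggests that this is intended.
- Naming the program whose value enters the test is a detail commonly left to a statistical analysis plan. None is at hand here, so its absence from the protocol is not a defect.

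**Conclusion.** No change to the plan is needed. The *or* in section 7.3 is best taken as a clerical slip: it is the lone outlier, it sits in a section about timing, and the analysis sections agree with each other. An analyst following 5.4.1 and 14.2 would use both programs in the same way for every ovary.

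The word at issue has little effect. Read exclusively, and with each woman's ovaries kept in one program, it leaves the paired t-test free of any constant offset. It could widen the between-woman SD by about 3-12% for assumed offsets of 0.5-1 SD, on an objective for which the protocol states no test. The possible inflation to about 5.6-7.9% does not come from this word. It also requires an assumed 5% level, two separate values per ovary, imperfect agreement between programs and selective reporting, none of which the protocol establishes. The setting is a 30-participant feasibility pilot, and the test serves a secondary objective.

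This conclusion would weaken only if 7.3 were actually applied as an exclusive choice, with a woman's two ovaries split between programs or the program picked after results were seen.

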7.4 Image data will be analyzed as they become available

8.0 INCLUSION AND EXCLUSION CRITERIA

8.1 Inclusion Criteria

8.2.1 Patients attending a preoperative visit at the Center for Comprehensive Gynecology who will undergo surgery.

8.2 Exclusion Criteria

8.2.1 Not able to comprehend and sign a written consent

8.2.2 Patients with a history of allergy to iodides

8.2.3 Patients history of renal failure or uremia, and those on dialysis

9.0 PARTICIPANT POPULATION(S)

We plan to recruit, consent and enroll 30 participants. Prior studies in colorectal surgery that demonstrated the safety and feasibility of intraoperative use of ICG for assessment of tissue perfusion included over 100 patients. With this pilot study, we aim to lay the foundation for future studies of ovarian vascular perfusion using intravenous ICG.

10. RECRUITMENT METHODS

10.1 Patients who are scheduled to undergo surgery at Northwestern Memorial Hospital will be approached for recruitment in the study at their preoperative visit in the Center for Comprehensive Gynecology clinic.

STU#: 00208846

10.2 Research coordinator will review consent form with potential participant leaving ample time for participants to review, comprehend and ask any questions about the consent form or the study. Consent will be reviewed in person when possible or reviewed in telehealth pre-op appointment using eConsenting process on REDCap.

11.0 WITHDRAWAL OF PARTICIPANTS

Patients can be taken off the study treatment and/or study at any time at their own request, or they may be withdrawn at the discretion of the investigator for safety, behavioral or administrative reasons. The reason(s) for discontinuation will be documented and may include:

11.1 Patient voluntarily withdraws from the study (follow-up permitted);

11.2 Patient withdraws consent (termination of treatment and follow-up);

11.3 Patient is unable to comply with protocol requirements;

11.4 Patient experiences toxicity that makes continuation in the protocol unsafe;

11.5 Treating physician will judge continuation on the study would not be in the patient's best interest;

11.6 Lost to follow-up. If a research subject decides against undergoing the surgical procedure and/or surgical case is cancelled, the subject may be considered lost to follow up.

12.0 RISKS TO PARTICIPANTS

12.1 All patients will be closely monitored by physician and nursing staff in the operating room and postoperative recovery area for the full duration of action of the ICG injection. ICG is considered a safe, well-studied medication.

12.2 Adverse Events

Rare adverse events include allergic reactions that range from urticarial (hives) to anaphylaxis. Because of the sodium iodide presence in ICG contraindications include patients with a history of allergy to iodides due to the risk of anaphylaxis (KARL STORZ Endoscopy – America, 2016). Because the patients will be under general anesthesia as is standard protocol for laparoscopy, the surgical and anesthesia teams will be able to easily manage any adverse reactions.

12.3 Drug interactions

Listed drug interactions include preparations containing sodium bisulfite which reduce the absorption peak of ICG (KARL STORZ Endoscopy - America, 2016)

Atropine; Hyoscyamine; Phenobarbital; Scopolamine: (Moderate) Phenobarbital may increase the clearance indocyanine green. The half-life of indocyanine green was lower in patients taking the drugs concomitantly compared to patients with normal and abnormal liver function taking no concomitant medications. The mechanism of interaction is unclear; those proposed in the medical literature include increased indocyanine green uptake by the liver cell, enhanced binding by specific hepatic carrier proteins, or more rapid excretion into bile.

Belladonna Alkaloids; Ergotamine; Phenobarbital: (Moderate) Phenobarbital may increase the clearance indocyanine green. The half-life of indocyanine green was lower in patients taking

STU#: 00208846

the drugs concomitantly compared to patients with normal and abnormal liver function taking no concomitant medications. The mechanism of interaction is unclear; those proposed in the medical literature include increased indocyanine green uptake by the liver cell, enhanced binding by specific hepatic carrier proteins, or more rapid excretion into bile.

Haloperidol: (Moderate) Haloperidol may increase the clearance of indocyanine green. The half-life of indocyanine green was lower in patients taking the drugs concomitantly compared to patients with normal and abnormal liver function taking no concomitant medications. The mechanism of interaction is unclear; those proposed in the medical literature include increased indocyanine green uptake by the liver cell, enhanced binding by specific hepatic carrier proteins, or more rapid excretion into bile.

Heparin: (Moderate) Heparin products that contain sodium bisulfite may reduce the absorption peak of indocyanine green. Collection of blood samples for analysis should be performed with anticoagulants that do not contain sodium bisulfite.

Hydrochlorothiazide, HCTZ; Propranolol: (Minor) In a study of 9 healthy adults given 0.5 mg/kg of indocyanine green, propranolol decreased clearance by 21%.

Nifedipine: (Moderate) In a study of 9 healthy adults given 0.5 mg/kg of indocyanine green, nifedipine increased indocyanine green clearance by 14%.

Nitrofurantoin: (Moderate) Nitrofurantoin may increase the clearance of indocyanine green. The half-life of indocyanine green was lower in patients taking the drugs concomitantly compared to patients with normal and abnormal liver function taking no concomitant medications. The mechanism of interaction is unclear; those proposed in the medical literature include increased indocyanine green uptake by the liver cell, enhanced binding by specific hepatic carrier proteins, or more rapid excretion into bile.

Phenobarbital: (Moderate) Phenobarbital may increase the clearance indocyanine green. The half-life of indocyanine green was lower in patients taking the drugs concomitantly compared to patients with normal and abnormal liver function taking no concomitant medications. The mechanism of interaction is unclear; those proposed in the medical literature include increased indocyanine green uptake by the liver cell, enhanced binding by specific hepatic carrier proteins, or more rapid excretion into bile.

Primidone: (Moderate) Primidone may increase the clearance indocyanine green. The half-life of indocyanine green was lower in patients taking the drugs concomitantly compared to patients with normal and abnormal liver function taking no concomitant medications. The mechanism of interaction is unclear; those proposed in the medical literature include increased indocyanine green uptake by the liver cell, enhanced binding by specific hepatic carrier proteins, or more rapid excretion into bile.

Propranolol: (Minor) In a study of 9 healthy adults given 0.5 mg/kg of indocyanine green, propranolol decreased clearance by 21%.

